9.3. Sample Size Determination

Assuming a 30% VH 0 response rate for DE-109 440 μ g group and a 12% response rate for the sham treatment group, 160 subjects (80 subjects per arm) is required to achieve 80% power to detect such a difference in response rate between the DE-109 440 μ g group and the sham treatment group using the Pearson's Chi-square test (two-sided, $\alpha = 0.05$). Including approximately 40 subjects in the dummy arm, a total of approximately 200 subjects with active NIU-PS will be randomized in a 2:2:1 ratio to DE-109 440 μ g, sham, and dummy arms.

9.4. **Populations for Analyses**

The following analysis populations for study analyses are defined: Full Analysis Set (FAS), Safety, Per-Protocol (PP), Intent-to-Taper, Macular Edema, Vision 20/40 or Worse:

- The **FAS population** will consist of all study eyes that are randomized and received at least one administration of study treatment. The FAS population will be the analysis population for the primary analysis and will use treatment as randomized.
- For analyses of ocular AEs and safety parameters assessed per eye, the **Safety population** will consist of all study eyes which received at least one administration of IP. For analyses of non-ocular AEs and safety parameters assessed per subject, the **Safety population** will consist of all subjects who received at least one administration of IP.
- The **PP population** will be a subset of the FAS population. The PP population will be the analysis population for sensitivity analyses and will use treatment as randomized. Any study eye affected by a significant protocol deviation (such that the outcome to treatment could be altered) will be excluded from the PP population. In addition, any study eye without the Month 5 VH score will be excluded from the PP population. Eyes to be excluded from the PP population will be identified before the unmasking of treatment assignments.

- The Intent-to-Taper population will be a subset of the FAS population, consisting of study eyes from subjects who were taking systemic (oral) corticosteroids at a stable prednisone-equivalent dose between ≥15 mg/day and ≤40 mg/day for at least 1 week (7 days) prior to and including on Day 1. The Intent-to-Taper population will be used for the analysis of tapering success performed using eyes as randomized.
- The Macular Edema population will be a subset of the FAS population and will consist of study eyes with $CST \ge 300$ microns at baseline.

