9.5.1. Handling of Missing Values

In the analysis of VH 0, VH 0 or 2-unit decrease (improvement), and VH 0 or 0.5+ responses:

- Subjects who (a) receive rescue therapy for conditions other than worsening of uveitis or (b) are rescued due to the worsening of uveitis but do not meet the protocol-defined rescue criteria, missing VH scores subsequent to receiving rescue therapy will be imputed using a multiple imputation-based approach before receiving rescue therapy.
- Missing VH scores of subjects not rescued before Month 5/Month 3 visit will be imputed using a multiple imputation-based approach.

The multiple imputation model will include vitreous haze measures at preceding visits and baseline characteristics. The response status will then be determined based on the observed or imputed VH scores.

No imputation is needed for composite score analysis as eyes with missing VH scores will be assigned a score of zero, unless they are rescued due to the worsening of uveitis or discontinued from the study due to lack of efficacy or adverse event (which will be assigned with a score of -1).

For medical events including AEs, completely or partially missing onset and resolution dates will be imputed in a conservative fashion to be detailed in the SAP. The same rules will be followed to impute completely or partially missing start and end dates of non-study medications.

Unless specified otherwise, descriptive summaries will be based on observed cases. No imputation of missing scores will be implemented.

Additional details on handling of missing data and sensitivity analyses on imputation methods will be provided in the SAP.

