5. GENERAL CONSIDERATIONS

All measures will be summarized descriptively. Continuous variables will be summarized using descriptive statistics such as number of observations (n), mean, standard deviation, standard error, median, minimum, and maximum. Categorical variables will be tabulated using frequency (n) and percent (%).

Unless otherwise specified, the following conventions will be followed in reporting the decimal places.

Reporting Statistics	Decimal Places
Range (Low Value, High Value)	Recorded Decimal Places
Mean, Median	Recorded value + 1 Decimal Places
Confidence Interval, Standard Deviation, Standard Error	Recorded value + 2 Decimal Places
P-value	4 Decimal Places (ex. 0.0021)

The statistical testing will be conducted at a significance level of 0.05 (two-sided) and the 95% confidence interval will be shown, unless specified otherwise. No statistical testing will be conducted for safety measures.

All data manipulations, descriptive summaries, and statistical hypothesis testing will be performed using Statistical Analysis System (SAS) Version 9.4 or later. Individual data, including relevant derived variables, will be listed.

Additional analyses not specified in this SAP may be conducted if deemed necessary and will be documented in the CSR.

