Study eyes which were rescued due to worsening of uveitis specified under previous protocol version but did not meet the rescue criteria under the current version will be treated as rescued due to other reason and censored the data after being rescued. The multiple imputation-based approach will be applied to impute missing VH score data of study eyes which were not rescued and treated as non-responders. The VH 0 response status will then be determined based on the observed or imputed VH score.

For missing VH score due to any other reasons other than protocol-specified worsening of uveitis, the multiple imputation approach will be applied as follows:

- 1. Use Markov chain Monte Carlo (MCMC) to create monotone missingness first with VH score on the logarithm scale. Then obtain standard multiple imputations under MAR assumptions for missing VH scores using monotone regression on the logarithm scale. The imputed values will be then converted into an eligible VH score based on the absolute distance. The missing data are filled in and 50 complete datasets are created. The seed that will be used in the SAS program is 135711.
- 2. Each of 50 complete datasets will then be analyzed separately. The CMH test statistic, response rate for each treatment group, and the rate difference will be calculated for each complete sets.
- 3. The final CMH test statistic, obtained from each complete dataset, will be transformed using Wilson-Hilferty transformation and combined for inference purposes (O'Kelly et al., 2014). Rates and rate differences will also be combined without any transformations.

The Mantel-Haenszel weighted response rate (%) of each treatment group, the Mantel-Haenszel weighted rate difference, the corresponding asymptotic 95% confidence interval (CI) and the CMH's p-value will be reported.

The main part of the SAS code for the specified CMH test procedure and the multiple imputation are provided in Appendix C, respectively.

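### As described, the primary imputation model leaves out the randomised arm, which shrinks the VH 0 rate difference among imputed eyes and costs some power

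*Protocol*

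**What the plan says.** Protocol 9.5.1 describes the model in one sentence: "The multiple imputation model will include vitreous haze measures at preceding visits and baseline characteristics". It then defers to the SAP: "Additional details on handling of missing data and sensitivity analyses on imputation methods will be provided in the SAP".

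SAP 8.2.1 supplies the mechanics. MCMC first makes the missingness monotone on log VH, and then: "Then obtain standard multiple imputations under MAR assumptions for missing VH scores using monotone regression on the logarithm scale". It fixes 50 datasets and a seed. It lists no covariates, names no treatment term and does not say that imputation is run by arm. It refers to an Appendix C for the SAS code, but the SAP's contents list shows only Appendices A and B.

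Not every failing or missing eye is imputed. Under SAP 5.2.1 and 8.2.1, an eye becomes a non-responder if it was rescued for protocol-specified worsening, if it met those criteria without rescue, or if its subject left the study because of inefficacy or an adverse event. Imputation covers the remaining missing scores, including those censored after rescue for other reasons.

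The same imputation serves the interim (SAP 5.5.1), Month 3 VH 0 response and the other VH response endpoints (SAP 5.2.1, 8.2.3, 8.2.4.1), and the treatment-policy analysis (SAP 8.2.2). Composite scores are not imputed.

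**The concern.** The primary test compares arms. If the model that fills in Month 5 haze has no arm term, it assumes that two eyes with the same earlier haze and baseline characteristics have the same Month 5 distribution, whichever treatment they received. Any treatment effect not yet visible in the earlier scores is then removed from the imputed eyes.

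The SAP names treatment in its other models: the GEE in 8.2.2 and the MMRM in 8.2.4.2 both include treatment and treatment-by-visit. The primary imputation does not.

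The planned sensitivity analyses do not correct this. The tipping-point analysis starts from the same MAR imputation and then worsens the treatment group's imputed values, which moves further toward no difference. The treatment-policy analysis reuses the model. LOCF avoids it, but only as a sensitivity analysis. At the interim, SAP 5.5.1 also admits subjects who have only reached Month 3, so the share of Month 5 values imputed could be larger than at the final analysis, and conditional power there drives the futility and sample-size decisions.

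**Working it through.** **1. Reproduce the planned size.** Inputs from Protocol 9.3: 30% on DE-109 440 µg, "a 12% response rate for the sham treatment group", and "160 subjects (80 subjects per arm) is required to achieve 80% power", at two-sided 0.05. With p̄ = 0.21 and the pooled formula:

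n = [1.96·√(2·0.21·0.79) + 0.8416·√(0.30·0.70 + 0.12·0.88)]² / 0.18² = (1.129 + 0.473)² / 0.0324 = 79.2, so 80 per arm.

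Power at n = 80 is Φ[(0.18·√80 − 1.129) / 0.562] = 80.4%. The plan's figure reproduces.

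**2. Limiting case.** Suppose earlier haze carried no arm effect. Eyes imputed without arm would then sit at a common 21% in both arms. With a share m imputed, the expected difference is 18·(1 − m) points. Power without arm uses the diluted rates at n = 80. Power with arm keeps the 18 points and takes 80·(1 − m) observed eyes per arm as the information, an approximation.

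| m (assumed) | Difference without arm | Power without arm | Power with arm | Loss due to omitting arm |
|---|---|---|---|---|
| 5% | 17.1 | 76.1% | 78.3% | 2.2 points |
| 10% | 16.2 | 71.5% | 76.1% | 4.6 points |
| 20% | 14.4 | 61.0% | 71.0% | 10.0 points |

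A separate multiple-imputation simulation (correlation 0.6, 80 per arm, 600 runs, last visit seen Month 1 to Month 4) gave 78% with arm and 76% without at 5% imputed, and 76% and 71% at 10%.

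**3. Allow earlier haze to carry part of the effect.** The model does contain haze at preceding visits. The check used latent-normal haze with first-order autoregressive correlation 0.6, Month 5 rates of 30% and 12%, and regression imputation without arm. Differences among imputed eyes were:

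- Effect growing linearly to Month 5: 0.5, 1.8, 4.3 and 9.4 points when the last visit seen is Month 1, 2, 3 and 4.
- Full effect from the first post-baseline visit: 4.7 to 12.2 points.

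Rounded, that is about 1 to 12 points, against a true 18. Adding arm to the regression restored 18 points within simulation error in every scenario.

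**4. Overall difference at 10% imputed.** 0.9·18 + 0.1·1 = 16.3 points, and 0.9·18 + 0.1·12 = 17.4 points.

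**5. Other correlations.** With one earlier visit already showing the full effect, imputed rates without arm were 24.3% and 17.6% (correlation 0.3), 25.9% and 16.1% (0.5), and 27.5% and 14.3% (0.7). The overall difference at 10% imputed was 16.9, 17.2 and 17.5 points. Some dilution remains each time.

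**The case against.** The strongest reply is that omission is not proved. The protocol sentence says what the model will include, not that nothing else may enter; the section presents itself as a summary and defers to the SAP; and the missing appendix is where a by-arm statement would appear. That stands as far as it goes: a reader might infer that the plan excludes arm, and neither document says so. But neither document puts arm in, and a programmer following the text has no instruction to add it.

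Other stronger readings also go too far:

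- A reader might infer that imputed eyes in both arms are pulled to one common rate. Post-baseline haze is in the model and carries some of the effect, so a common rate is only the limiting case.
- A reader might charge the whole fall from 80% power to omitting arm. At 10% imputed, power is already about 76% with arm included, because data are missing.
- A reader might infer that the other study eye's haze is excluded, or that it is the best available predictor. The protocol's wording is not limited to one eye, and the documents give no data on its predictive value.

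The final-analysis effect may also be small. Protocol 7.2 expects few withdrawals, and many failures are set to non-responder and never imputed. The calculations use one eye per subject, whereas SAP 3.3 expects two-eye subjects to lift power above 80%. The bias is toward no difference, so it cannot create a false positive. These points limit the size but do not remove the shrinkage.

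**Conclusion.** The concern holds as a gap in the imputation model that has a definite direction and is easily closed. Run as described, the model omits the randomised arm and biases the primary VH 0 rate difference toward zero. At 10% imputed, the overall difference is about 16.3 to 17.4 points instead of 18. The power loss due to omitting arm is about 2 points at 5% imputed and up to about 5 at 10%. Type I error is not inflated.

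These sizes rest on the planned 30% and 12%, a correlation of 0.6, the two effect shapes tried, one eye per subject and an assumed imputed share. The documents give no imputed share; larger shares would raise the loss.

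**What to change.** In SAP 8.2.1, state that VH is imputed separately by randomised arm, or with arm in both the MCMC and the monotone regression steps. List the covariates and supply Appendix C. Align Protocol 9.5.1 with this. Fitting by arm also stops dummy-arm eyes from informing the 440 µg or sham imputations; allocation is "randomized in a 2:2:1 ratio", so otherwise up to a fifth of subjects entering the model could come from an arm outside the primary comparison. Apply the same model at the interim, for Month 3 and the other VH responses, for the treatment-policy analysis, and as the start of the tipping-point analysis.

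The cost is a few sentences and a BY statement or extra model term, settled before unmasking. By-arm regressions are slightly less stable in smaller arms. If fitting is sparse, use arm as a covariate and say whether dummy-arm eyes enter.

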9.5.2. Efficacy Analyses

Rescue therapy is defined in Section 6.5.6 and is essentially any treatment that would have a therapeutic effect on NIU-PS other than intravitreal DE-109. Rescue therapy is permitted in the case of worsening of uveitis that satisfies protocol-defined rescue criteria. The use of rescue therapy is considered in assessing the VH response endpoints (VH 0 response, VH 0 or 2-unit improvement, and VH 0 or 0.5+ response). In the analysis of these endpoints at a specific follow-up visit (e.g., Month 5 or Month 3), subjects who met one of the protocol-defined rescue criteria will be assessed as non-responders regardless of whether the subjects were rescued or not.

Endpoint	Statistical Analysis Methods
Primary endpoint: VH 0 response ^a at Month 5	For the primary analysis of VH 0 response at Month 5, the Cochran-Mantel-Haenszel (CMH) test with Row Mean Scores statistic stratified by number of enrolled eyes from a subject (one eye or two eyes), baseline systemic (oral) corticosteroid use (yes or no), and region (US or non-US) will be conducted. Logistic generalized estimating equation (GEE) model, treatment policy strategy, last-observation-carried- forward (LOCF) imputation, and multiple imputation with tipping point analysis will be used as a sensitivity analysis.
 Secondary endpoints: Key secondary efficacy endpoints: Composite endpoint^b at Month 5 VH 0 response at Month 3 Composite endpoint at Month 3 	A hierarchical approach will be used to control the overall Type I error rate associated with the multiple comparisons across the primary and the key secondary efficacy endpoints. If the hypothesis testing for the primary endpoint successfully rejects the null hypothesis, the first key secondary efficacy endpoint will be tested, and so on. All the other secondary efficacy endpoints are supportive in nature. Therefore, no formal hypothesis testing will be performed on secondary efficacy endpoints. Two-sided 95% confidence intervals and nominal p-values may be reported for them, and such results will be interpreted descriptively in terms of the support they provide to the treatment comparisons for the primary and the key secondary efficacy endpoints in the sense of logical consistency.

Table 8:Endpoint Statistical A	Analysis
--------------------------------	----------

Endpoint	Statistical Analysis Methods	
Other secondary efficacy endpoints (double-masked period of study):	For secondary efficacy endpoints during double- masked period:	

^d VH 0 or 0.5+ response (remission of inflammation) is defined as a VH score of 0 or 0.5+ in the study eye at a specified follow-up visit based on the modified SUN scale.

^e Corticosteroid tapering success with resolution is defined as achievement of a prednisone-equivalent oral dose of 0 mg/day and a VH score of 0 in the study eye at a specified follow-up visit. This endpoint is assessed based on the Intent-to-Taper population (study eyes of subjects who received systemic [oral] corticosteroids at a stable prednisone-equivalent dose of between ≥ 15 mg/day and ≤ 40 mg/day that has remained stable for at least 1 week [7days] prior to and including on Day 1).

^f BCVA 3-line response is defined as an increase (improvement) of at least 3 lines (15 ETDRS letters) from baseline in BCVA at a specified follow-up visit. This endpoint is assessed based on eyes with a baseline best-corrected visual acuity (BCVA) ≤70 ETDRS letters (Snellen equivalent of 20/40 or worse).

9.5.3. Subpopulation Analyses

All the analyses listed in Section 9.5.2 will be repeated on the PP, Intent-to-Taper, Macular Edema, and Vision 20/40 or Worse sub-populations.

9.5.4. Safety Analyses

All safety analyses will be performed on the Safety Population.

Safety of DE-109 will be assessed by AEs and evaluation with slit-lamp biomicroscopy, indirect ophthalmoscopy, BCVA, intraocular pressure (IOP), fundus photography, fluorescein angiography, laboratory tests (serum chemistry, hematology, and urinalysis), physical examinations and vital signs.

Besides the overall summary of AEs, subjects with any AE(s) will be tabulated by system organ class (SOC) and preferred term specified in MedDRA dictionary. They will also be tabulated by SOC, preferred term, and maximum severity. For AE tables, a subject who experienced multiple AEs within a SOC or preferred term will be counted only once at the maximum severity for that SOC or preferred term. SAEs will be tabulated similarly. Separate summaries for ocular AEs and non-ocular AEs will also be performed. Ocular AEs will be summarized for study eyes and fellow eyes separately. Any ocular AE that occurred simultaneously to both eyes will be counted once for both the study eye and the fellow eye. Injection-procedure related AEs will be tabulated by SOC and preferred term.

AEs leading to death, SAEs, and AEs leading to discontinuation, if any, will be listed separately. Events of special interest will be listed by type of event. For other safety variables, descriptive summaries of observed score or status, change or shift from baseline, and/or change after injection, whichever applicable, will be performed.

9.6. Interim Analyses, Primary Analysis, and Analysis of Open-Label Period of Study

An interim analysis is planned when the first 100 subjects complete their Month 5 Visit. There are two goals for this interim analysis (1) to assess for futility; and (2) to re-assess the sample size. Sample size re-assessment will be performed with the "promising zone" approach as follows (Mehta et al., 2011). If the conditional power at the interim analysis is between 50% and 80%, the suggested sample size increase may be up to 100 subjects (i.e., 50% of the original sample size). If, on the other hand, the conditional power is > 80% or < 50%, no change to the sample size will take place. If the conditional power is < 30%, then the DMC could recommend stopping the trial due to futility. The DMC could recommend stopping the trial due to safety concerns at any of the DMC meetings and the interim analysis of unmasked data and the DMC will review the results and make recommendations based on the findings. The planned interim analysis will be specified in greater detail in the SAP and in the DMC charter.

The primary analysis of this study is the analysis of the data from the 6-month, double-masked period. These data will be quality-checked, soft-locked, and the primary analysis will be conducted after all subjects have completed the Month 6 visit or prematurely discontinued from the study prior to Month 6. An interim clinical study report will be written documenting the primary analysis results.

Analysis of the open-label period of the study will be performed after the end of the study and documented in the final clinical study report.

9.6.1. Data Monitoring Committee (DMC)

An independent data monitoring committee (DMC) whose members will not be participating in the LUMINA study conduct will serve as an advisory board to the Santen senior management team. The DMC will periodically review and make recommendations based on interim data; unmasked data will only be reviewed in closed DMC sessions without participation of Santen personnel. The organization, responsibilities, and procedures of the DMC will be specified in a governing charter.
10. SUPPORTING DOCUMENTATION AND OPERATIONAL CONSIDERATIONS

10.1. Regulatory, Ethical, and Study Oversight Considerations

10.1.1. Regulatory and Ethical Considerations

- This study will be conducted in accordance with the protocol and with the following:
 - Consensus ethical principles derived from international guidelines including the Declaration of Helsinki (Declaration_of_Helsinki, 2008) and Council for International Organizations of Medical Sciences (CIOMS) International Ethical Guidelines (CIOMS_Ethical_Guidelines, 2016).
 - Applicable ICH Good Clinical Practice (GCP) Guidelines
 - Applicable laws and regulations

10.1.2. Obligations of Investigators

In summary, the clinical investigator has agreed to the following obligations:

- Obtaining signed and dated informed consent from every subject prior to the subject's participation in any study related activity and maintaining records of consent as part of the study records.
- Obtaining approval from the Institutional Review Board/Independent Ethics Committee (IRB/IEC) and ensuring a copy of the letter indicating IRB/IEC approval is available at the investigational site before involving any subject in any study related activity; submitting verification of the approval to the Sponsor. Providing written summaries of the status of the study to the IRB/IEC annually or more frequently in accordance with the requirements, policies, and procedures established by the IRB/IEC. Submitting the final report to IRB/IEC and to the Sponsor.
- Approving the protocol and conducting the study according to the protocol and applicable regulations; informing the Sponsor of all deviations from the protocol.
- Informing the IRB/IEC of all protocol amendments/modifications and obtaining approval for the amendment/modification from the IRB/IEC in accordance with local requirements before implementation of changes made to the study design, except for changes necessary to eliminate an immediate hazard to study subjects; sending the Sponsor a copy of the letter from the IRB/IEC approving the amendment/modification.
- Reporting to the Sponsor and the IRB/IEC any SAEs or other significant safety findings that occur in the course of the investigation.
- Providing oversight of the conduct of the study at the site and adherence to requirements of 21 CFR, ICH guidelines, the IRB/IEC, and all other applicable local regulations.

- Keeping careful and accurate records of all clinical study data (study records must be considerably more exact and complete than those kept in ordinary medical practice); maintaining records of all materials submitted to the IRB/IEC study including the subject consent form and recruitment materials; maintaining records of all actions by the IRB/IEC regarding the study.
- Making study records available for inspection by the Sponsor (Santen) and representatives of the FDA and other regulatory agencies; keeping records until notified by the Sponsor that they may be destroyed.
- Maintaining proper control and documentation of all test and control articles.
- Submitting the following records and reporting to the Sponsor:

I. Prior to the Beginning of the Study

- A signed Form FDA-1572, Statement of Investigator.
- A current curriculum vitae (CV) if not submitted to Santen previously or if updated.
- CVs for all sub-investigators listed on the 1572.
- A letter from the Institutional Review Board/Independent Ethics Committee (IRB/IEC) indicating that the protocol was approved, including the name and address of the IRB/IEC.
- A copy of the consent form approved by IRB/IEC.
- A list of current members of the IRB/IEC.
- Financial disclosure (Section 10.1.3).

II. While the Study Is in Progress

- Acknowledgment of receipt of the test and control articles; documentation of disposition of all test and control articles.
- Original Case Report Forms for each subject enrolled in the study.
- Information regarding all deviations from the protocol.
- Information regarding all adverse medical events occurring to a subject while enrolled in the study.
- Annual progress report (if study is ongoing for more than one year). Letter from the IRB/IEC indicating approval of the annual progress report.

III. Once the Study Is Completed

- Disposition of all used and/or unused test and control articles, as well as documentation of all drug accountability.
- A final study report.

